12.2 Device Storage and Stability

Devices are to be stored in a secure/locked location and in accordance with the catheter and cable IFU. Do not use the (disposable) devices after the "Use By" date.

12.3 Device Preparation

Information related to device preparation can be found in the IFU.

12.4 Instructions for Use

A comprehensive set of IFU for the study devices and all accessory cables/interface cables is contained in each product package and is also available upon request.

12.5 Device Description and Specific Considerations

The investigational study devices are indicated in Figure 1.

[REDACTED]

[REDACTED]

[REDACTED]

[REDACTED]

[REDACTED]

[REDACTED]

12.6 Additional Equipment

12.6.1 System Components and Setup

[figure not shown]

The following devices, which may be CE marked by other companies, may also be required for the procedure:

- [Redacted list item]

Figure 2: Connectivity diagram for system set-up

[Redacted]	[Redacted]	[Redacted]	[Redacted]
[Redacted]	[Redacted]	[Redacted]	[Redacted]
[Redacted]	[Redacted]	[Redacted]	[Redacted]
[Redacted]	[Redacted]	[Redacted]	[Redacted]

criteria. Sites will be instructed to screen all subjects who require a documented ablation procedure for a cardiac arrhythmia in scope of the protocol, without regard to sex or race.

The study investigator or designated member of the research team will obtain written informed consent from the subject. The patient informed consent procedure must be done within 60 days before the actual study procedure takes place. The background of the proposed study and the potential benefits and risks of the study should be explained to the subject. The subject or legal representative must sign the consent form prior to any study-specific exams or tests are provided to them that fall outside of the standard of care. The consent form used must have prior approval from the CAs and study site's EC. Failure to obtain informed consent renders the subject ineligible for participation in the study.

The investigator and/or designee must also clearly document the process of obtaining informed consent in the subject's source documents. The voluntary process of informed consent confirms the subject's willingness to participate in the study. It's the investigator's responsibility to ensure that the informed consent process is performed in accordance with International Conference on Harmonization-Good Clinical Practices (ICH-GCP) and with applicable local and national regulations. If new information becomes available that can significantly affect a subject's future health and/or medical care, this information shall be provided to the subject(s) affected in written form. If relevant, all affected subjects shall be asked to confirm their continuing informed consent in writing by, dating and signing an amended ICF.

Each subject screened for enrollment in the clinical investigation who signs the patient ICF will be enrolled into the study. No subject should undergo any clinical investigation specific tests or examinations that fall outside the standard of care without first signing the patient ICF for this clinical investigation.

14.2 Baseline Evaluation and Procedures

14.2.1 Pre-Procedure/Baseline Assessments

Below pre-procedure assessments and data collection must be performed prior to the ablation procedure.

Within 60 days prior to the study procedure:

- **Baseline Medical, Cardiac History** (including findings from TTM, ECG, Holter monitor, etc.)
- **Transthoracic Echocardiogram (TTE)** – imaging to assess ejection fraction
Note: Available imaging within 6 months prior to the procedure (TTE or other acceptable equivalent cardiac imaging – i.e. CT/MRI) can be used to assess the LVEF. In case the imaging assessment is older than 6 months LVEF shall be re-assessed prior to insertion of the study catheter. In case the re-measurements before study catheter insertion fail to meet the LVEF criteria, the subject will be considered as not meeting eligibility and will be excluded.

Within 7 days prior to the study procedure:

Cardiac CT – imaging to assess the cardiac anatomy
Note: An available Cardiac CT, obtained within 60 days prior to the procedure, with a segmentable LA and LV compatible with CARTOMERGE™ can be used as reference when analyzing the CARTO™ and GE Vivid™ S70N data. In case the CT data is older than 60 days, or not compatible with CARTOMERGE™, a new CT should be obtained prior to the start of the study procedure.

- **Pregnancy Test** – only performed on women of child-bearing potential

All adverse events observed/reported after enrollment (ICF signed) should be collected and reported to the sponsor and ethics committee, as appropriate.

14.2.2 Study Procedure

Subjects will arrive to the electrophysiology laboratory for their study procedure and will undergo preparation for the procedure per the hospital's standard protocol (discretion of investigator)

Overall Use of the Investigational Device

During study procedures, investigators will use the investigational catheter instead of the institution's standard ultrasound catheter choice (e.g. SOUNDSTAR™). Any use of a non-investigational ultrasound device will be considered a failure of the primary performance endpoint.

The use of the investigational NUVISION™ NAV Ultrasound Catheter is **mandatory** for:

- Thrombus detection and LA/LV imaging for volume measurement at the start of the procedure;
- During transeptal puncture;
- And as navigational ULS catheter throughout the procedure.

Imaging guidance for LA/LV volume measurements:

- Capture preferably the full chamber in one ULS volumetric segment, if needed several segments can be taken.
- For capturing of the LA:
 - Capture 4D ULS clip (full 90°x90°) of the LA (with PVs and LAA) taken from the RA.
 - Repeat the acquisition from 3-6 slightly different positions, where the LA volume is partial.
Note: Capture 4D ULS clip before transeptal and insertion of any other catheters to the LA, by using the default ULS settings, and without using the "zoom" function.
 - Place the investigational NUVISION™ NAV Ultrasound Catheter near the interatrial septum and make sure to capture the ENTIRE left atrium.
 - Confirm by seeing both anterior-posterior and Roof to Mitral valve planes.
 - Make sure to allow sufficient ULS depth by visualizing the distal LAA.
- For capturing of the LV:
 - The catheter can be positioned either in the RA near the inferior septum or in the right ventricle (RV) near the interventricular septum.
 - Make sure to allow sufficient ULS depth by visualizing the entire chamber from the Mitral valve to the distal apex.

Investigators should use the CARTO™ 3 system to **"bookmark"** instances of abnormal study catheter "imaging noises". This will allow for further analysis of the data.

Standard of Care Ablation Procedure

Treatment will be per institution's standard of care (SOC).

14.2.3 Collection of Procedure Data for Post-Analysis (non-SOC)

At the completion of the study procedure, two back-up copies of the CARTO™ 3 and GE Vivid™ S70N Ultrasound Console system files will be made. One copy should be kept at the site within the investigator site or patient binders, and one anonymized copy will be provided to/collected by the Sponsor. Also, an anonymized copy of cardiac CT images will be collected to be used as reference when analyzing the CARTO™ and GE Vivid™ S70N data.

14.2.4 Data Collection during Study Ablation Procedure

Procedural parameters collected during the procedure include but are not limited to:

- Anatomical structures assessed
- Imaging for Left Atrium (LA) and Left Ventricle (LV) volume measurements
- Total fluoroscopy time
- Total procedure duration.

Following each procedure, physician feedback on the investigational catheter and associated software used will be collected, using a 7-point Likert-scale survey; it will include feedback on deployment, maneuverability, navigational features and imaging quality acquired. The survey will be entered into the eCRF for analysis.

14.2.5 Pre-Discharge Assessments

Once the investigator has achieved desired treatment results, the subject will be monitored as per the institution standard of care (post procedure practice) and subject will be discharged from the hospital in accordance with the hospitals standard procedures.

Before hospital discharge, any adverse events that have occurred since the procedure should be documented, entered into the eCRF, and reported, as appropriate.

14.3 Post-procedure Follow-up Schedule

All subjects will be contacted 7-days post-procedure via telephone call or by attending a clinic visit to assess for any adverse events. The window for this remote or in-clinic visit is +2 days (7-9 days). Alternative contact methods are allowed in case a telephone call or clinic visit is not feasible (*e.g.* telemedicine or mail contact). The method of contact should be documented in the eCRF.

At the 7-day follow-up visit, the following assessment will be performed:

- Adverse events (from the time of the procedure up until the visit)

14.4 Early Termination Visit

If early termination of the study is required due to safety concerns, each site will undergo a monitoring visit to conclude any outstanding issues, collect all outstanding CRF information, verify device accountability, and discuss any other items relevant to the conclusion of the study. Any enrolled subject will continue to be followed per the study protocol requirements. In case

of early termination due to safety concerns, reporting to EC and CA may be required per local regulations.

14.5 Unscheduled Visit

If a subject returns for a potential study related cardiovascular visit outside of the protocol-defined visit schedule provided in table 2, the visit will be considered “unscheduled” (UNS). An investigator may request an unscheduled visit in the presence of a new or worsened cardiovascular condition. For this study, unscheduled visits are recorded in the eCRF linked to the next scheduled study visit per clinical investigational plan.

14.6 Core Laboratory for Evaluation

No core labs will be used for this study.

14.7 Schedule of Events Table

Table 2 displays the required schedule for subject treatments and evaluations.

Table 2: Summary of Subject Visits and Assessments

Assessments ¹	Screening / Baseline (Clinic Visit)	Study Procedure	Discharge	7-day Follow-up (Clinic Visit or Phone call)
Informed Consent ²	✓			
Demographics	✓			
Medical and Cardiac History ³	✓			
Transthoracic Echo (TTE) ^{4,8}	✓			
Cardiac CT ^{5,8}	✓			
Pregnancy Test ^{6,8}	✓			
Thrombus detection ⁷		✓		
Adverse Events ⁹	✓	✓	✓	✓

- Standard of care assessments can be performed before ICF signature
- Informed consent to be signed **within the 60 days prior to procedure**
- Medical history-including but not limited to arrhythmia, heart disease and thromboembolic events
- TTE to determine the LVEF % **within the 60 days prior to procedure** (if the subject has undergone imaging in the last 6 months where the requested values were assessed, the assessment is not required)
- Cardiac CT for assessment of cardiac anatomy within 7 days prior to procedure (if the subject has undergone a CARTOMERGE™ compatible CT within 60 days of the procedure, the assessment is not required)
- Pregnancy tests for women of child-bearing potential only **within the 7 days prior to procedure**
- Thrombus detection, to rule out the presence of thrombus – **mandatory to be performed with the investigational catheter during the study procedure**
- Assessment should not be repeated for the study if already done per standard of care within the protocol defined time limits.
- AEs must be collected from the time the subject signs the informed consent onward.

15. Assessment of Safety

15.1 Specific Safety Parameters

15.1.1 Definition of Adverse Events (AE)

An AE is any untoward medical occurrence in a subject whether or not related to the investigational device.

Specifically, an AE is **any** undesirable experience (sign, symptom, illness, abnormal laboratory value, or other medical event) occurring to a subject during the course of the study, whether or not it is related to the investigational device or procedure. Physical findings (including vital signs) observed at follow-up, or pre-existing physical findings that worsen compared to baseline are considered AEs.

Any medical condition that is present at the time that the participant is screened will be considered as baseline and not reported as an AE. Such conditions should be added to background medical history, if not previously reported. However, if the study participant's condition deteriorates at any time during the study, it will be recorded as an AE.

Arrhythmia recurrence by itself is considered a recurrence of disease (pre-existing condition), and, therefore, **does not meet the definition of an AE.**

15.1.2 Definition of Serious Adverse Event (SAE)

A SAE is any event that meets one or more of the following criteria:

- Leads to death
- Leads to a serious deterioration in the health of a subject that resulted in:
 - A life-threatening illness or injury
 - An injury or permanent impairment of a body structure or a body function
 - In-patient hospitalization or prolongation of an existing hospitalization*
 - Medical or surgical intervention to prevent life-threatening illness or injury or permanent impairment to body structure or a body function
 - Chronic disease
- Leads to fetal distress, fetal death or a congenital abnormality or birth defect.

*Planned hospitalization for a condition present prior to the participant's enrollment in the study will not meet the definition of an SAE. An AE would meet the criterion of "hospitalization" if the event necessitated an admission to a health care facility (e.g., an overnight stay). Emergency room visits that do not result in admission to the hospital should be evaluated for one of the other serious outcomes.

15.1.3 Adverse Device Effect / Serious Adverse Device Effect

An adverse device effect is an AE related to the use of the investigational medical device.

NOTE 1- This includes any AE resulting from insufficiencies or inadequacies in the IFU, the deployment, the implantation, the installation, the operation, or any malfunction of the investigational medical device.

NOTE 2- This includes any event that is a result of a use error or intentional abnormal use of the investigational medical device.

A Serious Adverse Device Effect is an adverse device effect that has resulted in any of the consequences characteristic of an SAE.

15.1.4 Unanticipated (Serious) Adverse Device Effect

An Unanticipated Adverse Device Effect (UADE) or Unanticipated Serious Adverse Device Effect (USADE) is any SAE on health, safety, any life-threatening problem, or death caused by, or associated with a device, if that effect, problem, or death was not previously identified in nature, severity, or degree of occurrence in the investigational plan or risk analysis report, or any other unanticipated serious problem associated with a device that relates to rights, safety, or welfare of subjects. Refer to table 6 for a comprehensive list of foreseeable and anticipated AEs.

15.1.5 Study Device Deficiency

A device deficiency means any inadequacy in the identity, quality, durability, reliability, usability, safety or performance, including of an investigational device, including

- Malfunction (failure to perform in accordance to its intended purpose when used in accordance with the IFU/Clinical Investigational Plan (CIP)/IB),
- Use errors,
- Inadequacy in information supplied by the manufacturer.

If a device failure is detected or suspected, it should be documented on the appropriate eCRF and device failure and AE must be reported per section 0 AE documentation and reporting requirements.

15.2 Classification of an Adverse Event

15.2.1 Severity of Event

The intensity or severity of each AE must be assessed according to the following classifications:

Table 3: Intensity or Severity Definitions

Mild	Awareness of signs, symptoms, or events that are otherwise easily tolerated that may result in minimal transient impairment of a body function or damage to a body structure, but do not require intervention other than monitoring.
Moderate	Any event that results in moderate transient impairment of a body function or damage to a body structure that causes interference with usual activities, or that warrants possible intervention, such as the administration of medication, to prevent permanent impairment of a body function or damage to a body structure.
Severe	Any event that is incapacitating (an inability to do usual activities) or is life-threatening and results in permanent impairment of a body function or damage to a body structure, or requires intervention, such as major surgery, to prevent permanent impairment of a body function or damage to a body structure.

15.2.2 Relationship to Study Device

For all collected AEs, the clinician who examines and evaluates the participant will determine the AEs causality based on temporal relationship and his/her clinical judgment. The degree of certainty about causality will be graded using the categories below as described per Medical Device Regulation (MDR)

Table 4: Adverse Event Causality Classifications

Caused By	Relation	Definition of Relation
Device	Definitely (Causal Relationship)	The event is associated with the investigational device beyond reasonable doubt
	Probable	The relationship with the use of the investigational device seems relevant and/or the event cannot be reasonably explained by another cause, but additional information may be obtained
	Possibly	The relationship with the use of the investigational device is weak but cannot be ruled out completely. Cases where relatedness cannot be assessed, or no information has been obtained should also be classified as possible
	Not related	Relationship to the investigational device can be excluded
Study Procedure	Definitely (Causal Relationship)	The event is associated with the study procedure beyond reasonable doubt
	Probable	The relationship with the study procedure seems relevant and/or the event cannot be reasonably explained by another cause, but additional information may be obtained
	Possibly	The relationship with the study procedure is weak but cannot be ruled out completely. Cases where relatedness cannot be assessed, or no information has been obtained should also be classified as possible
	Not related	Relationship to the procedure can be excluded

15.2.3 Outcome

The outcome of each AE must be assessed according to the following classifications:

Table 5: Adverse Event Outcome Classifications

Classification		Definition
Resolved without sequelae		Subject fully recovered with no observable residual effects
Resolved with sequelae		Subject recovered with observable residual effects
Ongoing	Improved	Subject's condition improved, but residual effects remain
	Unchanged	AE is ongoing without changes in the overall condition
	Worsened	Subject's overall condition worsened
Death		Subject died as a result of the AE (whether or not the AE is related to the device or procedure)

15.2.4 Expectedness (Anticipatedness)

An anticipated AE is an effect which by nature, occurrence, severity or outcome has been identified as a possible complication associated with the investigational medical device and/or intervention procedure.

Potential AEs that are reasonably anticipated to occur during the cardiac EP procedure are listed in table 6. These events should be reported via EDC as anticipated AEs. Anticipated AEs are to be reported to the sponsor via EDC as indicated in section 0.

Table 6: Comprehensive List of Anticipated Adverse Events

Anticipated Adverse Events	
(Acute) renal failure	Hypoxia
(Aspiration) pneumonia	Increased phosphokinase level
(Skin) laceration	Infection, localized
(Vascular) bleeding	Infection, systemic
Acute Respiratory Distress Syndrome (ARDS)	Ischemia
Air embolism	Local Hematoma/ecchymosis
Allergic reaction to contrast media	Localized skin reaction
Allergic skin reaction	Mitral Insufficiency
Altered Mental Status Confusion; Altered Level of Consciousness;	Myocardial infarction with or without ST elevation
Anemia	Nausea
Anesthesia complications/reactions	Palpitations
Anoxic or hypoxic encephalopathy	Papillary Muscle tear/injury
Aortic Puncture	Pericardial effusion resulting in tamponade
Apnea - sedation induced	Pericardial effusion without tamponade
Arrhythmia (new or worsening of pre-existing arrhythmia)	Pericarditis
Asymptomatic Cerebral Emboli	(Periesophageal) vagal nerve injury
Atelectasis	Peripheral nerve injury
Atrial fibrillation	Phlebitis
Atrial Septal Defect (acquired)	Phrenic nerve damage/injury
Atrio-Esophageal fistula and/or injury	Pleural effusion
AV fistula	Pneumothorax
Back Pain	Post- and perioperative pain
Bronchial fistula, Broncho-pericardium fistula	Post Procedural Hematuria
Cardiac arrest	Pseudoaneurysm
Cardiac pacemaker insertion or replacement	Pulmonary edema
Cardiac perforation	Pulmonary embolism
Cardiac Tissue Injury	Pulmonary hypertension
Cardiac Valve Rupture/Damage	Pulmonary toxicity, like acute pulmonary syndrome
Cardiogenic Shock	Pulmonary vein dissection
Cerebro-Vascular accident (CVA)/Stroke	Pulmonary vein stenosis
Chest pain/discomfort	Renal Artery Stenosis
Complete or incomplete heart block	Respiratory arrest
Conduction block	Respiratory depression
Coronary Artery Stenosis	Respiratory failure
Coronary artery thrombosis	Respiratory infection
Death	Retinal Artery Embolism

Deep venous thrombosis	Retroperitoneal bleeding
Diaphragmatic paralysis	Sepsis
Dislodgement/Malfunction of pacemaker/defibrillator leads	Sinus bradycardia
Disseminated Intravascular Coagulation	Sinus tachycardia
Dizziness, presyncope, vertigo	Skin burn or necrosis
Dysphagia	Skin edema
Dyspnea	Skin or soft tissue (radiation) injury/tear
Endocarditis	ST segment changes
Epigastric Distress	Subclavian artery puncture
Epistaxis	Temperature elevation / Fever
Esophageal injury / perforation	Thrombocytopenia
Fatigue	Thromboembolism
Fluid overload	Thrombosis
Gastric hypomotility	Transient extremity numbness
Gastroesophageal reflux	Transient Ischemic attack (TIA)
Gastrointestinal disorders	Urinary Retention Postoperative
Gastrointestinal diverticulosis	Urinary tract injury or infection related to the urinary catheter
Gastroparesis	Valvular damage/insufficiency
Headache	Vascular (access) dissection (including coronary arteries)
Heart failure (acute or chronic)	Vascular Injury
Heart injury	Vascular occlusion
Heart valve insufficiency	Vascular Perforation
Hemoptysis	Vasovagal reactions
Hemorrhage	Ventricular Fibrillation
Hemothorax	Vessel damage/trauma
High/increased creatine phosphokinase (CPK)	Vessel perforation
Hypertension	Vessel spasm (including coronary arteries)
Hypervolemia	Visual disturbance
Hypotension	Worsening of pre-existing pulmonary disease
Hypovolemia	Wound healing disturbance

*Recurrence and exacerbation of an existing arrhythmia are anticipated adverse events. However, they will not be captured as such under this protocol, as they are considered recurrence of disease.

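### Protocol 15.1.1 and the Table 6 footnote disagree on whether exacerbation of an existing arrhythmia is an AE, and neither exemption excludes episodes suspected to be provoked by the investigational catheter

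*Protocol*

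**What the plan says.** Protocol 15.1.1 treats conditions present at screening as baseline, but adds that if the subject's "condition deteriorates at any time during the study, it will be recorded as an AE". It then makes one exception: "Arrhythmia recurrence by itself is considered a recurrence of disease (pre-existing condition"), which therefore does not count as an AE. Exacerbation is not mentioned in that exception.

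Protocol 15.2.4 says of the events in Table 6: "These events should be reported via EDC as anticipated AEs". One entry in the table is "Arrhythmia (new or worsening of pre-existing arrhythmia"). The footnote under the table reads: "Recurrence and exacerbation of an existing arrhythmia are anticipated adverse events. However, they will not be captured as such under this protocol". Its stated reason is that both count as return of the disease. The footnote covers exacerbation as well as recurrence, and it does not carry the qualifier *by itself*.

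Protocol 6.4.1 lists arrhythmia caused by manipulating an ICE catheter as a known risk, at <0.2%. By inclusion criterion 1 (9.1), every subject enters with an arrhythmia.

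The SAP analyses catheter-related SAEs (8.5) and catheter-related non-serious AEs (8.6). It neither restates nor resolves the exemption.

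**The concern.** There are two problems. First, a site that follows 15.1.1 records an exacerbation of the subject's arrhythmia as an AE, while a site that follows the footnote does not. Each can cite protocol text.

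Second, the exemption is justified as return of the disease. That reason does not fit an episode that the investigational catheter may have provoked, yet neither text excludes such an episode. If it is not captured as an AE, nobody is required to grade its relation to the device. It can then be absent from the primary endpoint (related SAEs) or from the secondary endpoint of related non-serious AEs. This is a first-in-human study whose primary safety endpoint is device-related harm, so the capture rule should not depend on which page a site reads.

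**Working it through.** No planned figure depends on this point, so there is none to reproduce. The check is a comparison of the texts, followed by a bound on size.

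**1. The texts side by side**

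| Text | Recurrence | Exacerbation or worsening | Catheter-suspected episode |
|---|---|---|---|
| 15.1.1, deterioration rule | not addressed separately | AE | not addressed separately |
| 15.1.1, arrhythmia exception | not an AE, if *by itself* | not mentioned, so the deterioration rule applies | no exclusion stated |
| Table 6 arrhythmia entry | not mentioned | anticipated AE, to be reported | not mentioned |
| Table 6 footnote | not captured | not captured | no exclusion stated |

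On recurrence, 15.1.1 and the footnote agree, and that choice is not disputed here. On exacerbation they disagree. Whether the Table 6 entry is a further conflict cannot be settled, because the place in the table to which the footnote's asterisk belongs is not visible in the text.

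**2. Routes by which a catheter-provoked episode of the subject's own arrhythmia could be captured**

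- *As an adverse device effect (15.1.3).* "An adverse device effect is an AE related to the use of the investigational medical device". An event that is not an AE does not qualify by this route.
- *Through causality grading (15.2.2).* Grading applies to AEs that have been collected. The rule in Protocol 20.4.6 and SAP 8.5, under which every grade except unrelated counts as related, therefore cannot recover an event that was never collected.
- *Through use error.* NOTE 2 in 15.1.3 says: "This includes any event that is a result of a use error or intentional abnormal use of the investigational medical device". Use errors are also device deficiencies (15.1.5), reported under 15.4.4 and listed under 20.4.7 and SAP 8.6. That listing does not feed the safety endpoints.
- *Through seriousness (15.1.2).* "A SAE is any event that meets one or more of the following criteria". A serious episode may be captured here, and *by itself* in 15.1.1 may point the same way. The protocol does not say whether this definition prevails over the exemption.
- *Through symptoms or consequences.* Table 6 separately lists palpitations, dizziness, chest pain and hypotension, and also heart failure, cardiogenic shock, ventricular fibrillation and cardiac arrest. These remain reportable, as do new arrhythmias.

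What clearly remains uncaptured is a non-serious, symptom-free episode without use error.

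**3. Size**

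Inputs: 30 subjects (Protocol 20.2, SAP 7) and <0.2% for ICE-related arrhythmia (Protocol 6.4.1, no unit given). Assumption: 0.2% is an upper bound per subject, and all 30 subjects are in the Safety Analysis Set.

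- Expected events: below 30 × 0.002 = 0.06.
- Chance of at least one: below 1 − (1 − 0.002)^30 = 5.8%.
- Effect of one omitted event: 1/30 = 3.3% would be reported as 0/30 = 0%.

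The 0.2% covers all ICE-related arrhythmia, including new arrhythmias that stay reportable. The affected subset is smaller, and the documents do not allow it to be computed.

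**The case against.** The strongest reply is that the texts form a hierarchy. The deterioration rule is general, the arrhythmia sentence is a specific exception, and the footnote explains that exacerbation belongs to the same exempt category. On that reading there is no conflict, only a clarification in an awkward place. It is a possible reading, but the protocol does not state it. The exception in 15.1.1 is limited to recurrence by itself, and a footnote that removes the limit and adds a second kind of event changes the rule.

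A second reply is that an arrhythmia provoked mechanically is not return of the disease by itself, so the exemption never reached it. This too is arguable from 15.1.1, but the footnote lacks the qualifier. The Safety Management Plan (15.5), which was not available, may settle the matter; if it does, the protocol should say so.

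Three parts of the opposing case stand in full. The Table 6 entry cannot be counted as a proven contradiction: if the asterisk sits on it, the entry and the footnote are simply a rule and its exception. Symptomatic episodes can reach the endpoints through the separately listed symptoms. And any remedy must not treat every arrhythmia during the procedure as suspected, because 14.2.2 requires the catheter to be used throughout the procedure.

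A reader might also infer that catheter-provoked arrhythmia as a whole escapes the safety endpoints, or that the primary endpoint is bound to be undercounted. The documents do not support either inference, given the routes for new arrhythmias, symptoms, clinical consequences, use error and possibly serious episodes.

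**Conclusion.** The concern holds in a limited form. Section 15.1.1 and the Table 6 footnote give different answers for exacerbation and must be reconciled. Neither exemption excludes episodes of the subject's own arrhythmia suspected to be provoked by the investigational catheter, so such episodes can be left out of the catheter-related safety endpoints. The gap is clear for a non-serious, symptom-free episode without use error. For a serious episode it is only possible, because the precedence of 15.1.2 is not stated.

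This is a minor correction. Fewer than 0.06 events are expected in 30 subjects, on the assumption that the <0.2% is a per-subject rate, and the affected share is smaller still. The analyses are descriptive, and no hypothesis test or success threshold is affected.

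**What to change.** - Align 15.1.1, the Table 6 arrhythmia entry and the footnote into one rule that covers both recurrence and exacerbation.
- State that the exemption does not apply when the investigator documents a specific reason to suspect the investigational catheter. An example is onset immediately on manipulating that catheter or touching tissue with it. Onset merely while the catheter is in use should not be enough.
- Record such episodes as AEs and grade them for seriousness and relatedness under the existing rules. Ordinary early recurrence stays exempt.
- State whether 15.1.2 prevails over the exemption for serious episodes. Either answer is workable once it is written down.

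The cost is a wording change in 15.1.1, 15.1.2, Table 6 and its footnote, an eCRF completion note, and some additional AE records and causality assessments. Cases whose cause cannot be settled are graded *Possibly* under Table 4 and so count as related, in the primary endpoint if serious and in the secondary endpoint if not. In the primary endpoint each affected subject adds 1/30, or 3.3 percentage points. The planned summary by level of relationship (Protocol 20.4.6, SAP 8.5) shows these cases separately.
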